### **Procedures for Investigator to Withdraw Subjects**

Indications to halt active participation of the subject in the GH study

1. PI or any regulatory authority (IRB, or FDA) believe withdrawal is necessary for the subject's health, well-being, or best interests.
2. PI or any regulatory authority believe that withdrawal is necessary for the subject's health, well-being, or best interests
3. Laboratory: any abnormality on any test with adverse event (AE, Common Terminology Criteria for Adverse Events, National Cancer Institute, scales) # 3 or greater at any time in the study
4. Any AE of any sort (clinical, laboratory) # 4 will result in halting for the individual and also for the study as a whole.

**Participants Will Be Recruited** Yes

**Recruitment Method(s)** Clinical Practice, Other Website

### **How Participants Will Be Identified**

All participants must be diagnosed with Phelan McDermid Syndrome.

Phenotype definition will be conducted using a comprehensive assessment battery, including: (1) psychiatric evaluation; (2) clinical genetics evaluation; (3) neurological examination; (4) Vineland Adaptive Behavior Scales.

All patients must also have pathogenic deletions or mutations of the SHANK3 gene confirmed by array CGH and/or direct sequencing on record.

**Who Will Initially Approach Potential Participants** Study Personnel, Member of Primary Care Team, Treating Physician, Clinic Personnel

### **How Research Will Be Introduced to Participants**

Potential participants in the Seaver Autism Center outpatient clinic as well as families of patients with Phelan McDermid Syndrome will be informed about this study directly or via websites (such as Phelan McDermid Syndrome Foundation)

### **How Participants Will Be Screened**

Participants will be screened based on the inclusion criteria and a diagnosis of Phelan McDermid Syndrome and with open epiphyses as evidenced by a bone age x ray.

## **10. Subjects - Risk and Benefits**

### **Risks to Subjects**

Growth hormone will be administered as subcutaneous injections once daily by parent or guardian at home.

Blood draws will be done every 4 weeks during study and 4 weeks following study.

Potential adverse events from Growth Hormone(GH) are described in the package insert. Some adverse effects include headaches, myalgia, fluid retention, benign intracranial hypertension, slipped capital femoral epiphyses, insulin resistance and hypothyroidism. Local reactions include erythema or pain at injection site and lipoatrophy with long term use.

Patients will require to be seen by a physician at our center every 4 weeks for evaluations and monitoring safety.

### **Description of Procedures Taken to Lessen the Probability or Magnitude of Risks**

Participants suitable for the study will undergo comprehensive medical evaluation by the study psychiatrist. Medical history, family history, physical and neurological examination (including anthropometric measurements, fundoscopic exams), routine hematology and blood chemistry and X-ray will be performed at baseline. All families will be educated on appropriate growth hormone administration. Patients will be monitored for tolerability every 4 weeks throughout the study using physical and neurological and psychological evaluations (including anthropometric measurements, fundoscopic exams). This monitoring will occur at weeks 4, 8, and 12 and then again 4-weeks after study termination.

All testing will be scheduled at the same time as the four weekly visit in order to avoid inconveniencing patient.

### **Provisions for Research Related Harm / Injury**

Serial evaluations by physician every 4 weeks during study and also safety parameters monitored by blood draws will reduce research related harm/injury.

An adverse event (AE) will be defined as any untoward medical occurrence in a study subject, temporally associated with the use of the experimental medication, whether or not considered related to the medication. An adverse event can therefore be any unfavorable and unintended sign (including an abnormal laboratory finding), symptom, or disease (new or exacerbated) temporally associated with the use of the experimental medication. A serious adverse event (SAE) will be defined as an AE that meets any of the following criteria:

results in death;

is life threatening;

requires inpatient hospitalization;

results in a persistent or significant disability/incapacity;

any other adverse event that, based upon appropriate medical judgment, may jeopardize the subject's health and may require medical or surgical intervention to prevent one of the outcomes listed above.

### **Adverse Events Reporting**

The Principal Investigator (PI) will be responsible for the detection and documentation of events meeting the criteria and definition of an adverse event or serious adverse event, as provided in this protocol. During the study, when there is a safety evaluation, the investigator or team member will be responsible for reporting adverse events and serious adverse events. Each subject's parents/guardians will be instructed to contact the investigator immediately should the subject manifest any signs or symptoms they perceive as serious.

Clinical laboratory parameters and other abnormal assessments qualifying as adverse events and serious adverse events:

Abnormal laboratory findings or other abnormal assessments that are judged by the investigator to be clinically significant will be recorded as AEs or SAEs if they meet the definition of an AE. Clinically significant abnormal laboratory findings or other abnormal assessments that are detected during the study or are present at baseline and significantly worsen following the start of the study will be reported as AEs or SAEs. The investigator will exercise his or her medical and scientific judgment in deciding whether an abnormal laboratory finding or other abnormal assessment is clinically significant.

### **Medically attended visits**

For each AE the subject experiences, the subject's parents/guardians will be asked if they received medical attention defined as hospitalization, an emergency room visit or a visit to or from medical personnel (medical doctor/doctor of osteopathy or nurse practitioner) for any reason. This information will be recorded in the CRF (case report form).

#### Lack of Efficacy

Lack of efficacy per se will not be reported as an AE. The signs and symptoms or clinical sequelae resulting from lack of efficacy will be reported if they fulfill the AE or SAE definition (including clarifications).

#### Time Period, Frequency, and Method of Detecting AEs:

All AEs occurring from the initiation of therapy until 4 weeks following its completion will be recorded on the Adverse Event form in the subject's CRF, irrespective of severity or whether or not they are considered medication-related. Onset of chronic illness (e.g. autoimmune disorders, asthma, type 1 diabetes and allergies) and conditions prompting emergency room (ER) visits or physician office visits that are not related to well-child care, injury, or common acute illnesses (e.g., upper respiratory tract infection, otitis media, pharyngitis, and gastroenteritis) will be reported during the entire study period. The investigator will inquire about the occurrence of AEs at every visit/contact during the study and throughout the follow-up phase as appropriate. All AEs either observed by the investigator or a clinical collaborator or reported by the subject's parent/guardian spontaneously or in response to a direct question will be evaluated by the investigator. AEs not previously documented in the study will be recorded in the Adverse Event form within the subject's CRF. The nature of each event, date and time (where appropriate) of onset, outcome, intensity and relationship to drug administration should be established. Details of any corrective treatment should be recorded on the appropriate page of the CRF.

When an AE/SAE occurs, it will be the responsibility of the investigator to review all documentation (e.g., hospital progress notes, laboratory, and diagnostic reports) relative to the event. The investigator will then record all relevant information regarding an AE/SAE on the eCRF or SAE Report Form as applicable. The investigator will attempt to establish a diagnosis of the event based on signs, symptoms, and/or other clinical information.

**Safety:** To evaluate safety, participants will be assessed every 4 weeks by the study psychiatrist. There are a number of tertiary outcomes designed to monitor the safety of GH.

Monitoring for AEs will be conducted during scheduled and unscheduled visits per clinical and laboratory assessments. General AEs will be graded by the National Cancer Institute (NCI) CTCAE scales (note: please see discussion immediately following for AEs with neurological signs and symptoms). Examples of possible AE grades for parameters which will be measured during treatment (shown in Table 3 Research Protocol PDF). Also, any AE that the PI deems serious, although not easily categorized in the National Cancer Institute grading system, will be considered # grade 3.

If a subject develops significant (CTCAE AE # 3 grade) neurological signs and symptoms (e.g. cerebrovascular event or peripheral neuropathy), they will be seen immediately for a comprehensive evaluation, appropriate treatment, and removal from active participation in the study. We will also apply NCI-CTCAE criteria for attribution of AE by means of the following descriptors and codes, following the NCI guidelines for their application.

unrelated to treatment 1  
unlikely related to treatment 2  
possibly related to treatment 3  
probably related to treatment 4  
definitely related to treatment 5

The following are the potential adverse events associated with GH and how we intend to monitor and prevent these occurrences.

#### Slipped capital femoral epiphyses (SCFE)

SCFE is a potential adverse effect of growth hormone therapy. We will monitor for this by parental reporting of hip pain (unilateral or bilateral), limping or difficulty bearing weight. Children suspected of SCFE will undergo bilateral hip x-ray in a frog leg position for diagnosis.

#### Alterations in glucose homeostasis

Glucose homeostasis will be measured using hemoglobin A1C levels as well as glucose and insulin levels prior to and during therapy.

#### Increased intracranial pressure

In order to monitor for increased intracranial pressure, children will undergo fundoscopic examination.

#### Expected Direct Benefit to Subjects

Autism is a severe lifelong neuro-developmental disorder characterized by impairments in reciprocal social interaction, communication deficits and repetitive and restricted patterns of behavior and interests with onset in the first three years of life.

Our pilot study on use of IGF-1 in patients with Phelan McDermid syndrome showed improvement in the standardized Aberrant Behavior Checklist (ABC) and the Repetitive Behavior SubScale-Revised (RBS-R) after 12 weeks of therapy ([name], 2014).

Considering growth hormone acts via the IGF-1 pathway, this medication that is easily accessible and administered once daily (in comparison to twice daily IGF-1) should improve social withdrawal in this population. Growth hormone will also not produce hypoglycemia in patients that has been known to occur with IGF-1 use.

#### **Benefit to Society**

Growth hormone is a commercially available drug that has a good safety profile following decades of study. Growth hormone administration has been shown to improve mental and motor development in children with Prader Willi Syndrome owing to its impact on IGF-1 (Donze et al, 2018).

The success of this clinical trial could have implications on other genetic forms of autism spectrum disorder in the future. It will also provide more information to the healthcare community in this field.

#### **Provisions to Protect the Privacy Interests of Subjects**

Members of the research team may also provide clinical care to this population in the Seaver Autism Center; thus, it is acceptable and appropriate for the team to present the research to patients in the clinic. Patients recruited outside of the Seaver Autism Center will approach study personnel after viewing our ads and only if the family is willing will our research personnel discuss the study with family. We may conduct initial telephone conversations with these families to inform them regarding the study. Prospective subjects and their parents will be informed of and consented for the study in the privacy of an investigator's office during a clinic visit. Follow-up visits and phone calls made to subjects will be carried out in the context of clinical care.

It will be explained to the subject's parents that all questions asked and procedures performed will be part of the study, and they will be informed that they do not need to answer all of the questions or they can decline a procedure if they feel uncomfortable.

#### **Economic Impact on Subjects**

None

## **11. Subjects - Children**

**Select Which of the Following Best Describes the Risk Presented to Children**

- \* No greater than minimal risk to children is presented.*
- \* Greater than minimal risk to children and the research presents the prospect of direct benefit to the individual subjects.*
- \* Greater than minimal risk to children presented by an intervention or procedure that does not hold out the prospect of direct benefit for the individual subject, or by a monitoring procedure which is not likely to contribute to the well-being of the subject.*
- \* None of the above but the research presents a reasonable opportunity to further the understanding, prevention, or alleviation of a serious problem affecting the health or welfare of children.*

**Risk Presented to Children**

Greater Than Minimal Risk With Direct Benefit

## **12. Procedures - Narrative**

### **Description of the Study Design**

The proposed pilot will seek to recruit 20 children aged 2 to 12 years old with SHANK3 deletions or mutations and with radiographic evidence of open epiphyses. Phenotype definition will be conducted using a comprehensive assessment battery, including: (1) psychiatric evaluation; (2) clinical genetics evaluation; (3) neurological examination; (4) Vineland Adaptive Behavior Scales. The study will include newly recruited children in addition to those who have been previously recruited for the purposes of genetic studies by the Seaver Autism Center.

Patients recruited will have screening prior to trial and will then follow up at 4 weeks, 8 weeks and 12 weeks of therapy with growth hormone daily injections. A 4 week post therapy follow up will also be arranged.

Inclusion criteria:

Diagnosis: Pathogenic deletions or mutations of the SHANK3 gene confirmed by array CGH and/or direct sequencing.

Age Range: Cases will be between 2 and 12 years old at the time the phenotypic measures were collected.

Exclusion criteria:

Cases will be excluded if any of the following criteria are applicable:

closed epiphyses;

active or suspected neoplasia;

intracranial hypertension;

hepatic insufficiency;

renal insufficiency;

cardiomegaly/valvulopathy;

history of allergy to growth hormone or any component of the formulation (mecasermin);

history of extreme prematurity (<1000 grams) with associated early neo-natal complications, e.g. intra-cerebral hemorrhage, prolonged hypoxia, prolonged hypoglycemia;

patients with comorbid conditions who are deemed too medically compromised to tolerate the risk of experimental treatment with growth hormone.

Patient with visual problems that preclude the use of VEPs

### **Drug**

Growth hormone is secreted by the somatotrophs of the anterior pituitary gland in a pulsatile manner. It binds to its receptor, signaling a cascade of intracellular events which directly stimulated the synthesis and release of IGF-1. (Ashpole et al; 2014, Grimberg et al; 2016).

Growth hormone is FDA approved for use in children with growth hormone deficiency (including idiopathic [of unknown cause] growth hormone deficiency), Turner syndrome, Noonan syndrome, Prader-Willi syndrome, short stature homeobox-containing gene (SHOX) deficiency, chronic renal insufficiency, idiopathic short stature and children small for gestational age. (<https://www.fda.gov/Drugs/DrugSafety/ucm237839.htm>)

It is available in the form of several commercial preparations. This is typically available as a 10 mg vial to be reconstituted with in-package syringe of 1 mL of bacteriostatic water (preserved with 0.33% metacresol), and a 25G reconstitution needle.

### **Drug Administration**

Growth hormone will be administered subcutaneously once daily using a 12-week single group design. No placebo will be used. The 12-week duration was selected because of our previous trial with IGF-1 showing effects in standardized behavior scales in that duration, hence establishing proof of concept.

The dose of daily growth hormone varies with the indication for therapy. Approved doses of growth hormone range from 0.16-0.25mg/kg/week for growth hormone deficient patients (Grimberg et al.; 2016) and up to 0.47 mg/kg/week for patients born small for gestational age.

In our proposed trial, we expect a majority of our patients to be growth hormone sufficient and therefore similar to the population of children with idiopathic short stature treated with growth hormone. We will recommend a dose of 0.15mg/kg/week divided daily for 2 weeks as a starting dose to ensure safety and tolerance. The dose will then be increased to 0.3mg/kg/week for 10 weeks, an average growth hormone dose in children with idiopathic short stature.

The growth hormone dose will be titrated based on IGF-1 levels monitored serially up to a maximum dose of 0.45mg/kg/week. (<http://www.ferringusa.com/wp-content/uploads/2018/07/ZOMACTON-PI-7-18.pdf> )

Drug dose is calculated on a mg/kg/week basis. Using Center for Disease Control average Weight-for-age statistics in typically developing children ages 2 to 12 years ([www.cdc.gov/growthcharts/cdc\\_charts.htm](http://www.cdc.gov/growthcharts/cdc_charts.htm)), the overall average weight across a representative sample of males and females in this age range is 24.65kg.

Average growth hormone dose for weeks 1-2: 0.15mg \* 24.65kg per week = 3.7 mg per week

Average growth hormone dose for weeks 3-10: 0.3mg \* 24.65kg per week = 7.4 mg per week

With a recruitment target of 20 patients, we anticipate the need for a total of 1628 mg of growth hormone with each person requiring about 81 mg of growth hormone in 12 weeks. We anticipate the need for 17 vials of growth hormone (10 mg per vial).

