### **Safeguards to protect Subjects rights and welfare**

Participants suitable for the study will undergo comprehensive medical evaluation by the study psychiatrist. Medical history, family history, physical and neurological examination (including anthropometric measurements, fundoscopic exams), routine hematology and blood chemistry (including liver profile) and X-ray will be performed at baseline.

Patients will be monitored for tolerability every 4 weeks throughout the study using physical and neurological examination (including anthropometric measurements and fundoscopic exams). Patients will be monitored at weeks 4, 8, and 12 and then again 4-weeks after study termination with the following safety measures: physical and neurological examination (including anthropometric measurements and fundoscopic exams), routine hematology and blood chemistry.

Potential adverse events from Growth Hormone (GH) will be explained to participant's families and also be monitored for during their serial evaluations.

Informed consent shall be obtained from parents or legal guardians after a thorough explanation of the study protocol.

The study will be conducted according to Good Clinical Practice (GCP), the 1996 Declaration of Helsinki (Protocol Appendix A), (US 21 CFR Part 50—Protection of Human Subjects, and Park 56—Institutional Review Boards) and local rules and regulations of the country.

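### Every child's dose doubles after week 2 with no scheduled check that the starting dose was tolerated; a week-2 phone inquiry tied to the step would close the gap

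*Combined protocol and SAP*

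**What the plan says.** The dosing text in section 12, *Drug Administration*, reads: "We will recommend a dose of 0.15mg/kg/week divided daily for 2 weeks as a starting dose to ensure safety and tolerance". The next sentence begins: "The dose will then be increased to 0.3mg/kg/week for 10 weeks". The same two steps appear in section 22, *Selection Procedures to Minimize Toxicity*, and in section 25, *Justification for Meeting Criteria*. None of the three places attaches a condition to the increase.

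Sections 12 and 22 then add: "The growth hormone dose will be titrated based on IGF-1 levels monitored serially up to a maximum dose of 0.45mg/kg/week". The Lay Summary gives the IGF-1 target as 1 to 2 SD above the mean.

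The monitoring schedule is consistent wherever it is given:

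- Section 8, *Safeguards*: "Patients will be monitored for tolerability every 4 weeks throughout the study", by physical, neurological and fundoscopic examination.
- Section 10, *Procedures Taken to Lessen the Probability or Magnitude of Risks*: "This monitoring will occur at weeks 4, 8, and 12 and then again 4-weeks after study termination", and "All testing will be scheduled at the same time as the four weekly visit".
- Section 10, *Risks to Subjects*: "Blood draws will be done every 4 weeks during study and 4 weeks following study".
- Section 12, *Description of the Study Design*: recruited patients "will then follow up at 4 weeks, 8 weeks and 12 weeks of therapy".
- The safety paragraph at the end of section 10, *Time Period, Frequency, and Method of Detecting AEs*, and section 22, *Frequency of Data Review*, also use a four-week interval.

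Between visits, section 10 asks parents to contact the investigator about signs that they regard as serious, and it allows for unscheduled visits.

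**The concern.** The low starting dose is presented as a safety measure, and section 22 lists it among the steps that limit toxicity. Its protective value has two parts: lower exposure at the outset, and the chance to notice a child who does not tolerate the drug before more is given. The plan delivers the first. It makes no provision for the second, because nothing is scheduled between the first dose and the doubling and no finding is required before the dose goes up.

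What is at stake is modest but concerns patient safety. A child with mild early headache, swelling or limp would move to twice the dose unless a parent judged the sign serious enough to call. The visible text offers withdrawal or halting in response to adverse events, and titration in response to IGF-1. It describes no option to hold the dose for a child with a milder problem. If a sign is first recorded at week 4, it may also be unclear whether it began at 0.15 or at 0.3.

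**Working it through.** **1. Inputs.** From section 12, *Drug Administration*: 0.15 mg/kg/week for 2 weeks, then 0.3 for 10 weeks; average weight 24.65 kg; 20 children; stated need 1,628 mg, about 81 mg each; 10 mg per vial; 17 vials; maximum dose 0.45; cited approved doses from 0.16 to 0.47 mg/kg/week. From the schedule sections: on-treatment visits at weeks 4, 8 and 12.

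**2. The plan's own figure.**

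- Weekly dose: 0.15 × 24.65 = 3.70 mg, then 0.30 × 24.65 = 7.40 mg.
- Per child: 2 × 3.7 + 10 × 7.4 = 81.4 mg.
- All children: 20 × 81.4 = 1,628 mg. This reproduces the stated total.

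The dose schedule is therefore 2 weeks plus 10 weeks, with the step at the end of week 2.

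**3. Step against schedule.**

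| Time | Dose event | Scheduled on-treatment check |
|---|---|---|
| Week 0 to 2 | 0.15 mg/kg/week | none |
| End of week 2 | rises to 0.30 | none |
| Week 4 | 0.30 continues | first visit, examination and blood draw |

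- Size of the step: 0.30 / 0.15 = 2.0, a doubling.
- Delay from step to first check: 4 − 2 = 2 weeks.
- Scheduled checks before the step: 0, for each of 20 children.

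**4. Exposure before the first check.**

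- 2 × 0.15 + 2 × 0.30 = 0.90 mg/kg, or 0.90 × 24.65 = 22.2 mg at the average weight.
- Share given at the doubled dose: 0.60 / 0.90 = 67%.
- Share of the planned course: 0.90 / (2 × 0.15 + 10 × 0.30) = 0.90 / 3.30 = 27%.

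These figures describe exposure. They do not measure harm, and the documents give no event rate from which harm could be estimated.

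**5. IGF-1.** No time points are given; the text says only that levels are followed serially. With draws every 4 weeks and all testing placed at the four-weekly visit, the first on-treatment value falls at week 4. That timing is an inference.

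**6. Cost of a hold.** A child kept at 0.15 until week 4 and then given 0.3 receives 4 × 0.15 + 8 × 0.30 = 3.0 mg/kg instead of 3.3, and 3.0 / 3.3 = 0.909, a loss of 9%. This applies only to children who are held, and it ignores later titration.

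**7. Two clerical points in the same text.**

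- 1,628 / 10 = 162.8, so at least 163 vials are needed. Seventeen vials hold 170 mg.
- The worked dose labels the second phase as weeks 3 to 10, which is 8 weeks. That would give 20 × (2 × 3.7 + 8 × 7.4) = 1,332 mg. The stated 1,628 mg needs weeks 3 to 12.

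**The case against.** The best defence is that the wording fits a gradual introduction and never promises a decision point. Starting low limits early exposure even if nobody looks. The starting dose is just below the lowest approved dose cited (0.16), 0.3 is described as average for idiopathic short stature, and the doubling is large in relative terms partly because the start is so low. In absolute terms it equals the later allowance from 0.3 to 0.45. All of this stands. It means the plan cannot be faulted for failing a test that it set itself, but it does not supply a check before the step.

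There is also cover between visits. Potential adverse events are explained to families, all events are recorded from the start of therapy, parents may report at any time, unscheduled visits exist, follow-up phone calls are mentioned in section 10 under privacy, and doubt about safety leads to withdrawal from treatment. This narrows the gap. None of it is scheduled at week 2 or made a condition of the increase.

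A reader might infer more than the documents support:

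- *That fundoscopy and blood tests must precede the step.* Nothing in the documents shows that moving to a mid-range approved dose needs them, and they would add a visit and a draw for every child.
- *That every child should stay at 0.15 until week 4.* This costs exposure in a 12-week study and delays titration. It is a debatable trade-off, not a correction.
- *That nothing can be detected before the doubling.* This is true only of scheduled checks.
- *That two early problems would end the trial.* Under section 22, *Primary or Secondary Safety Endpoints*, a halt ordinarily stops new screening and treatment starts, while unaffected enrolled children ordinarily continue.
- *That ten weeks at 0.3 forbids titration.* Sections 12 and 22 go on to provide for it, so this is loose wording.

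**Conclusion.** The point holds in a limited form. The dose doubles unconditionally at the end of week 2 for all 20 children, and the visible plan schedules no on-treatment contact before week 4. Tolerance of the starting dose is thus not checked before the step, apart from parent-initiated reports or unscheduled visits. This is a cheap improvement to patient safety. It is no evidence that the regimen is unsafe, and it does not affect the validity of the efficacy analysis.

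The conclusion assumes that the narrative schedule is complete. The Research Plan listed under Attachments was not available and could hold a week-2 contact. If it does, the protocol text should say so, because it now places all testing at the four-weekly visits. The absence of a scheduled contact before week 4 is explicit in the text; only the timing of the first on-treatment IGF-1 is inferred.

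**What to change.** In sections 12, 22 and 25, replace the unconditional increase with text such as:

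> At the end of week 2, study staff telephone the parent or guardian and make a structured adverse-event inquiry covering headache, vomiting, visual or behavioural change, oedema, limp or hip pain, and polyuria or polydipsia. The dose is raised to 0.3 mg/kg/week only if there is no event of grade 2 or higher judged at least possibly related to treatment. Otherwise the child stays at 0.15 mg/kg/week and is reassessed at the week-4 visit, or earlier at an unscheduled visit.

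Replace the fixed ten weeks at 0.3 with: thereafter, subject to IGF-1 titration. Section 25 does not currently mention titration, so the change also aligns the three places.

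The grade and relatedness thresholds are a proposal built on the protocol's own CTCAE grading and five-level attribution codes. The study physicians should confirm them.

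Cost: one call per child, 20 in all, with no extra visit or blood draw. A few children may stay at 0.15 for up to two more weeks, each losing about 9% of planned cumulative dose if then raised to 0.3 at week 4.

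Separately, correct 17 vials to at least 163, and change weeks 3 to 10 to weeks 3 to 12 in sections 12 and 22.
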